8.2.2.1.1 Marker of cell proliferation, Ki67

8.2.2.1.2 Molecular targets of metformin, including, in order of priority, pS6, pAKT^{S473}, p4EBP, pACC

8.2.2.2 Expression of frequent dysregulated molecular mechanisms and organic cation transporter 3 (OCT 3) in the target lesion and in the normal tissue, including, in order of priority, EGFR, pEGFR, p53, PTEN, pERK, p16, and OCT3. The expression of these biomarkers will be assessed in the baseline

and post-intervention biopsies to determine the biochemical consequences of the metformin treatment, and their potential relationship with the clinical response to metformin.

- 8.2.2.3 Targeted analysis of cancer-associated genes in the target lesion and blood DNA collected at baseline to determine the impact of genomic alterations on the biological and biochemical consequences and clinical response to metformin.
- 8.2.3 Serum and saliva based biomarkers
 - 8.2.3.1 Metformin effect on serum metabolic markers (C-peptide, glucose and HbA1c)
 - 8.2.3.2 Metformin concentrations in serum and saliva at baseline and post-intervention
 - 8.2.3.3 Metformin effect on serum and saliva inflammatory and angiogenic cytokines, including interleukin (IL)-6, IL-8, growth-related oncogene-1 (GRO-1), and vascular endothelial growth factor (VEGF). These cytokines will be measured in samples collected at baseline and post-intervention.
- 8.2.4 Exploratory Endpoints
 - 8.2.4.1 To characterize changes in the saliva microbiome before and after metformin intervention, including both the absolute microbial load and taxonomic composition.
 - 8.2.4.2 To evaluate the potential microbiome signatures that are correlated with treatment response.

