9. CORRELATIVE/SPECIAL STUDIES

9.1 Rationale for Methodology Selection

Tissue biomarkers, including Ki67, pS6, pAKT^{S473}, p4EBP, pACC, EGFR, pEGFR, p53, PTEN, pERK, p16, and OCT3 will be assessed by immunohistochemistry (IHC). IHC is the best and most validated

technique for measuring protein levels of the biomarkers of interest in paraffin-embedded tissue. It allows analyses of relative expression levels of each biomarker and determination of localization of each marker.

Serum and saliva metformin concentrations will be determined by chromatography-tandem mass spectrometry method, which provides high sensitivity and specificity for metformin analysis.

Serum and saliva inflammatory and angiogenic cytokines, including IL-6, IL-8, GRO-1, and VEGF, will be measured by Luminex Multianalyte System. Luminex™ technology allows for simultaneous quantification of multiple proteins in a single sample.

Genomic analyses will be conducted in blood DNA and DNA extracted from the target lesion by targeted sequencing using the current Expanded Solid Tumor Panel at the Center for Advanced Laboratory Medicine, University of California San Diego. This panel covers all exons for 399 genes, which is designed to detect hotspot mutations and key fusion of approximately 400 genes often associated with cancer progression, including oral cancer. Importantly, targeted sequencing has been applied successfully to DNA extracted from formalin-fixed paraffin-embedding tissue sections.

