13.3 Accrual and Feasibility

The study plans to accrue 26 eligible participants to initiate agent intervention. With a projected attrition rate of 20%, we anticipate to have at least 20 participants completing the agent intervention to provide study endpoint data. The planned duration of accrual is 24 months with the expected accrual rate of 1 per month among three study sites.

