13.5 Secondary Objectives, Endpoints, Analysis Plans

The secondary objectives of this study are to evaluate the histologic response to metformin intervention, to determine the metformin effect on cell proliferation and its molecular targets, to determine the metformin effect on frequent dysregulated molecular mechanisms and OCT expression, and to determine the impact of genomic alterations on the biological and biochemical consequences and clinical response to metformin.

Additional secondary objectives include evaluation of the metformin effect on serum metabolic markers, measurements of metformin concentrations in serum and saliva, and evaluation of metformin effect on serum and saliva inflammatory and angiogenic cytokines.

Similar to the primary endpoint, the histologic response rate will be calculated and a one-sided 95% confidence interval based on the exact method will be derived. Based on a small sample size of 20, nonparametric methods, e.g. signed rank test, will be performed to evaluate each of the changes in tissue, serum, and saliva markers. In addition, a univariate logistic regression model with the clinical response as the outcome variable will be fitted to explore if any of the expression of frequent dysregulated mechanisms, OCT3 levels, and any genomic alterations is associated with the clinical response to metformin.

To identify statistically significant changes in the saliva microbiome before and after metformin treatment, we will first evaluate changes in alpha diversity among matched pairs using non-parametric analogous Wilcoxon rank-sum test (Mann-Whitney test). To test for significant differences in beta diversity (e.g. if pre-treatment and post-treatment samples cluster in principle coordinates analysis space), permutational multivariate analysis of variance (PERMANOVA) will be used. Importantly, we are currently performing experiments in healthy volunteers to define the stability of the saliva microbiome over the course of a day

and in response to routine perturbations (e.g. brushing teeth, eating a meal). The results from these experiments will allow us to determine the appropriate effect size and assess potential correlations between the saliva microbiota and therapeutic outcome.

With an anticipated attrition rate of 20%, we will try to reduce the fraction of participants with missing outcomes as much as possible. Also, multiple imputation techniques will be used to handle missing data.

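### Section 13.5 regresses response on rare gene alterations in about 20 participants by logistic regression, where zero cells will be common, and names no estimator or test that copes with them

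*Combined protocol and SAP*

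**What the plan says.** Section 13.5 states that "a univariate logistic regression model with the clinical response as the outcome variable will be fitted", to explore whether the dysregulated-mechanism markers, OCT3 or "any genomic alterations is associated with the clinical response to metformin". The marker list in Section 8.2.2.2 is "EGFR, pEGFR, p53, PTEN, pERK, p16, and OCT3". For the genomic part, Section 9.1 says "This panel covers all exons for 399 genes", and Section 8.2.2.3 makes this a secondary endpoint, intended "to determine the impact of genomic alterations on the biological and biochemical consequences and clinical response to metformin".

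On numbers, Section 13.3 says "The study plans to accrue 26 eligible participants to initiate agent intervention" and "With a projected attrition rate of 20%, we anticipate to have at least 20 participants completing the agent intervention".

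Elsewhere in Section 13.5 the small sample is taken into account. Histologic response gets an exact interval, and the sentence just before the logistic model chooses its tests for marker changes accordingly: "Based on a small sample size of 20, nonparametric methods, e.g. signed rank test". For the logistic model, Section 13 gives no estimator, no test (Wald, likelihood-ratio or score), no penalised or exact method, no minimum number of carriers and no multiplicity rule. Sections 13.5 and 13.6 call for multiple imputation of missing data without saying how results will be pooled.

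**The concern.** A present/absent alteration carried by a few of 20 participants gives a sparse 2x2 table. If every carrier responds, or none does, the logistic likelihood has no finite maximum. Software then reports a very large coefficient with a far larger standard error, or stops without converging. The Wald p-value drifts to about 1 whatever the strength of the evidence, and no usable odds ratio or Wald interval can be reported.

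What is at stake is the secondary endpoint on genomic alterations and response. A gene whose carriers all responded could be listed as null under one software default and as a notable finding under another test from the same fit. Since the plan does not fix the test, that choice would be made after the data are seen.

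**Working it through.** **Inputs.** Evaluable n = 20 (Sections 13.3 and 13.5; 26 x 0.8 = 20.8). Benchmark response rates are 30% and 60% (Section 13.1), so 6 to 12 responders among 20. The panel has 399 genes (Section 9.1). Assumptions: each gene is coded altered or not altered, and carrier counts run from 1 to 5, because the documents give neither a coding rule nor alteration frequencies.

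**The plan's own figure.** No power or sample size is stated for the logistic analysis, so there is none to reproduce. The 87% power of the primary test does reproduce: declaring success at 10 or more responses of 20 gives an exact one-sided level of 0.0480 and power 0.8725.

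**Step 1: how often a zero cell occurs by chance.** For a gene with m carriers, unrelated to response, with R responders among 20 and m small:

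P(zero cell) = [C(R,m) + C(20-R,m)] / C(20,m)

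| Carriers m | R = 10 | R = 6 |
|---|---|---|
| 1 | 20/20 = 100% | 20/20 = 100% |
| 2 | 90/190 = 47% | 106/190 = 56% |
| 3 | 240/1140 = 21% | 384/1140 = 34% |
| 4 | 420/4845 = 9% | 1016/4845 = 21% |
| 5 | 504/15504 = 3% | 2008/15504 = 13% |

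With 8 or 12 responders, m = 2 gives (28 + 66)/190 = 49%.

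A simulation over assumed prevalences agrees. Among genes with at least one altered and one unaltered participant, 56-61% have a zero cell at 10% prevalence with no association. That rises to 83% with a true association of 90% versus 50% response.

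**Step 2: what the fit returns.** Take 5 of 5 carriers and 5 of 15 non-carriers responding.

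- Maximum likelihood: log odds ratio about 22.3, standard error about 13,073, so z is about 0.0017 and the Wald p-value 0.999. The exact values depend on where the software stops.
- Fisher, two-sided: 2 x C(10,5)/C(20,5) = 504/15504 = 0.033.
- Likelihood ratio: null log-likelihood 20 ln(0.5) = -13.863; fitted 5 ln(1/3) + 10 ln(2/3) = -9.548; statistic 2 x 4.315 = 8.63 on 1 df, p = 0.003.
- Firth penalised likelihood ratio: p = 0.011.

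For 6 of 6 against 4 of 14, the Wald p-value is 0.998, Fisher's is 420/38760 = 0.011 and the likelihood-ratio p-value is 0.0009.

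**Step 3: where the failure changes the conclusion.** With 10 responders, zero-cell tables with 1, 2, 3 and 4 carriers have Fisher p = 1.0, 0.47, 0.21 and 0.087. None reaches 5%, so a non-significant Wald result agrees with Fisher there. From 5 carriers the two part company. With 6 responders, 3 of 3 carriers responding gives Fisher p = 20/1140 = 0.0175, so disagreement starts at 3 carriers. With 8 or 12 responders, 3 carriers can reach 56/1140 = 0.049.

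**Step 4: where nothing fails.** A strong association without a zero cell behaves normally: 9/10 against 1/10 gives Wald p = 0.003 and Fisher p = 0.001. Normally distributed continuous scores rarely separate at n = 20: about 0% with no shift, under 1% with a 1 SD shift and 9-12% with a 2 SD shift.

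**The case against.** The strongest reply is that the plan names neither maximum likelihood nor the Wald test, and that the likelihood-ratio test from the same fit survives separation. Both points are correct. A reader might infer that the plan commits to a method that reports its strongest genes as null, or that the secondary objective cannot be answered. The documents do not support either reading: p-values near 1 belong to the Wald test, strong associations without a zero cell are unaffected, and most zero-cell tables with few carriers hold little evidence by any test.

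What remains is the unqualified model. Logistic regression with no further description ordinarily means maximum likelihood with Wald output. Even with a likelihood-ratio p-value, the odds ratio is infinite and its Wald interval unusable. The usual way of pooling multiply imputed fits combines estimates and standard errors, so it would meet the same divergence, though the plan does not state its pooling method.

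A reader might also infer about 20 chance hits from 399 x 0.05 = 19.95. That assumes every gene is testable at its nominal level. Unaltered genes are not tested at all, and sparsely altered ones often cannot reach 5% by an exact test, so the figure should not be used. The absence of a multiplicity rule still stands.

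Finally, the analysis is worded as exploratory, in a phase IIa trial whose signals would go to a phase III study (Section 2.2). That limits the consequence but does not remove it, since the analysis serves a listed secondary endpoint.

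**Conclusion.** The point holds as a weakness in one exploratory secondary analysis. With about 20 evaluable participants, zero cells will be routine for alterations carried by one to three people (21-100% by chance for 6 to 12 responders) and less common at four or five (3-21%). In those tables the standard odds ratio is infinite, and the p-value for identical data can be 0.999 or 0.003 depending on a test the plan leaves open. The effect on conclusions is confined to zero-cell tables with enough carriers to carry real evidence: from 3 carriers with 6, 8 or 12 responders, and from 5 with 10.

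This rests on present/absent coding, on assumed carrier counts, and on reading unqualified logistic regression as maximum likelihood. The primary binomial test and its 87% power are untouched, and continuous marker scores are little affected.

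**What to change.** In Section 13.5:

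- For present/absent alterations, replace logistic regression with Fisher's exact test and exact odds-ratio intervals, or with Firth regression and profile-likelihood intervals. Name one in advance.
- Test only genes whose carrier count could reach p<0.05 given the observed number of responders, and describe the rest. State this as a rule, not a fixed number: the floor is 3 carriers with 6, 8 or 12 responders, but 5 with 10. A fixed floor of 4 or 5 would discard testable genes in some cases, and a floor of 4 would admit untestable ones with 10 responders. The rule uses only the table margins, on which Fisher's test already conditions, so it does not inflate the error rate.
- Report Benjamini-Hochberg q-values across the tested genes and label the screen hypothesis-generating.
- Keep logistic regression for continuous IHC and OCT3 scores, with profile-likelihood or Firth inference if separation occurs.
- Say how the gene screen treats participants with missing response, since the general multiple-imputation statement does not settle it.

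The cost is SAP wording and a few lines of code, with no change to sample size or procedures. The downside is that rarely altered genes are described rather than tested.

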1.3 Exploratory Objectives

1.3.1 To characterize changes in the saliva microbiome before and after metformin intervention, including both the absolute microbial load and taxonomic composition

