7. CLINICAL EVALUATIONS AND PROCEDURES

7.1 Schedule of Events

Evaluation/ Procedure ¹	Baseline	Agent Start Day 1 of Week 1	Weeks 1-5	Week 6 (± 1 week)	Weeks 7-11	Week 12-14 or Early Termination	Follow-Up (2-4 weeks post- intervention)
Informed Consent	X						
Assess Eligibility	X						
Medical History	X			X		X	
Vital Signs ² / Height ³ and Weight	X			X		X	
Physical Exam ⁸	X			X		X	
Performance status	X						
Concomitant medications	X		X	X	X	X	X
Assessment of tobacco and alcohol use	X					X	
Fasting blood for CBC/diff, CMP ⁷ , C- peptide, HbA1c	X					X	
Urine pregnancy test if applicable	X	X ⁴		X		X	
Examination of oral cavity	X			X		X	
Lesion measurement	X			X		X	
Photography	X			X		X	
Biopsies ⁵	X					X	
Saliva collection for research biomarkers ¹⁰	X					X	
Fasting blood collection for research biomarkers	X					X	
Dispense Study Agent ⁴		X		X			
Collect Study Agent				X		X	
Review Agent Diary/Record				X		X	
Adverse Events			X	X	X	X	X
Telephone/Email Contact			X ⁶		X ⁹		X

¹ Initiation of study agent should occur within 9 weeks of baseline biopsy. On-study evaluations should be conducted with the following timeframes: week 6 interim visit can be scheduled +/- 1 week; total agent intervention duration is 12 – 14 weeks; post-intervention visit can be scheduled between weeks 12-14; the agent should be taken until the evening before the post-intervention visit.

² Vital signs include temperature, blood pressure, and pulse.

³ Only at baseline.

⁴ Eligible participants may have agent shipped to them. Urine pregnancy test for women of childbearing potential does not need to be repeated at agent start if the baseline test was done within 4 weeks prior to agent start.

⁵ At baseline, a biopsy will be performed on the lesion that meets the size criteria or on the largest lesion, if multiple lesions that meet the size criteria. If smaller lesions meet the size criteria and are of clinical concern to treating physician, they may be biopsied. The lesion with the worst histology following the central pathology review will be the target lesion and re-biopsied at post-intervention. If the target lesion is not visible post-intervention, a biopsy will be obtained at the site of the previous lesion biopsy. Biopsy of visually normal cheek mucosa will be obtained at baseline and post-intervention.

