13.2 Randomization/Stratification

This is a single-arm, open-label trial so no randomization, stratification or blocking will be performed. Also, no formal interim analysis is planned.

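### Section 13.5 names an unpaired test (Wilcoxon rank-sum, Mann-Whitney) for before/after saliva alpha diversity that the same sentence describes as matched pairs

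*Combined protocol and SAP*

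**What the plan says.** Exploratory objective 1.3.1 reads "To characterize changes in the saliva microbiome before and after metformin intervention", and section 8.2.4.1 repeats it as an endpoint. For alpha diversity, section 13.5 states "we will first evaluate changes in alpha diversity among matched pairs using non-parametric analogous Wilcoxon rank-sum test (Mann-Whitney test").

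The design leaves no second group to compare: section 13.2 says "This is a single-arm, open-label trial so no randomization, stratification or blocking will be performed". Sections 7.2 and 7.4 and the schedule in 7.1 have saliva taken from the same participants at baseline and at the week 12-14 visit. On numbers, section 13.3 says "we anticipate to have at least 20 participants completing the agent intervention to provide study endpoint data", out of 26 who start.

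For the other before/after measurements, an earlier paragraph of 13.5 says "nonparametric methods, e.g. signed rank test, will be performed to evaluate each of the changes in tissue, serum, and saliva markers". The signed rank test is a paired test.

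**The concern.** The sentence contradicts itself. The rank-sum and Mann-Whitney tests are the same procedure, and its null distribution assumes that the two samples are independent. Here the two samples come from the same people. An analyst must either discard the pairing to run the named test, or keep the pairing and depart from the plan.

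The likely harm is a missed change. When a participant's two values are positively correlated, differences between people that cancel in a paired comparison stay in the rank-sum test as noise. Its true error rate then falls below the nominal level, and power falls with it. A significant result would still stand. A null result would say little, because it could reflect only the choice of test.

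There is also a conduct issue. If the contradiction is left to be settled at analysis, the choice between two tests with possibly very different p-values is made after the data are seen.

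**Working it through.** **No planned figure to reproduce.** The documents give no power, level or effect size for the alpha-diversity test, so the check shows what the named test does to data of this structure.

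**Inputs from the documents.** One arm (13.2); saliva before and after in the same participants (7.1, 7.2, 7.4); about 20 complete pairs from 26 starters (13.3).

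**Assumptions, not in the documents.** Bivariate normal values with equal variance; two-sided 5% level; shift of 0.5 SD as one illustrative effect; within-person correlation ρ from 0 to 0.9. Section 13.5 mentions healthy-volunteer work to "define the stability of the saliva microbiome over the course of a day", but that concerns variation within a day. It does not supply a correlation across 12 weeks or more.

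**Step 1: why the size falls.** For n pairs with standard deviation σ, the variance of the mean difference is 2σ²(1 − ρ)/n. An unpaired comparison acts as if it were 2σ²/n. As a rough guide, the nominal cut-off of 1.96 then behaves like 1.96/√(1 − ρ):
- ρ = 0.3: 1.96/√0.7 = 2.34, two-sided tail about 1.9%
- ρ = 0.5: 1.96/√0.5 = 2.77, two-sided tail about 0.6%

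**Step 2: simulation.** 20 pairs, exact null distributions, 20,000 simulated trials per cell.

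| ρ | Rank-sum size | Rank-sum power | Signed-rank power |
|---|---|---|---|
| 0 | 5.1% | 32% | 31% |
| 0.1 | 4.2% | 31% | 33% |
| 0.2 | 3.1% | 30% | 37% |
| 0.3 | 2.1% | 30% | 42% |
| 0.5 | 0.8% | 27% | 55% |
| 0.7 | 0.1% | 24% | 76% |
| 0.9 | about 0% | 20% | 99.6% |

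The size of the signed-rank test stays between 4.7% and 5.1% throughout. The simulated rank-sum sizes of 2.1% and 0.8% agree with the rough values in step 1.

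**Step 3: other effect sizes, at ρ = 0.5.** Rank-sum against signed-rank power is about 3% against 13% for a 0.2 SD shift, 27% against 55% for 0.5 SD, and 72% against 91% for 0.8 SD. The direction is the same each time. Of these three, 0.5 SD gives the widest gap.

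**Step 4: a constructed extreme case.** Let 20 participants have baseline values 0, 1, …, 19, and let each rise by 0.50 + 0.01 × their baseline value, so that every rise lies between 0.50 and 0.69. The rank-sum p-value is 0.80. The exact signed-rank p-value is 2/2²⁰ = 0.0000019. Every participant rose, and the named test sees nothing.

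**Step 5: incomplete pairs.** The rank-sum test could use all 26 baseline samples against 20 post-intervention samples, while the signed-rank test uses only the 20 pairs. Power for a 0.5 SD shift (rank-sum by normal approximation, 6,000 simulated trials per cell):

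| ρ | Rank-sum, 26 and 20 | Signed-rank, 20 pairs |
|---|---|---|
| 0 | 36% | 31% |
| 0.1 | 35% | 33% |
| 0.2 | 35% | 37% |
| 0.3 | 34% | 42% |
| 0.5 | 32% | 55% |

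The two break even between ρ = 0.1 and ρ = 0.2.

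**The case against.** The strongest reply is that this is a slip of terminology. The sentence sets the task as change within pairs, its word for an analogue hints at the non-parametric counterpart of a paired test, and the same section uses the signed rank test as its example for other markers. The team evidently knows the right test and might well run it. The endpoint is also exploratory, no sample size or decision rule depends on it, and under positive correlation the error cannot produce a false claim.

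The limits on impact stand. The charitable reading does not remove the error: the text says rank-sum and then adds Mann-Whitney in parentheses, which identifies the unpaired test. The signed rank example covers the secondary markers, and the microbiome paragraph names its own test.

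Three points about the numbers also stand:
- The effect size is assumed. Section 13.5 leaves it to the healthy-volunteer work, so 0.5 SD is only an illustration.
- The tables cover non-negative correlations only. At ρ = −0.3 the rank-sum test would be too liberal, with size about 8%. Negative correlation between a person's own two samples is implausible here.
- Sections 13.5 and 13.6 plan multiple imputation for missing data, which the incomplete-pairs comparison does not model.

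None of these is a reason to keep a test that contradicts its own sentence.

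**Conclusion.** The concern holds. As written, section 13.5 prescribes an independent-samples test for paired data, and no other section corrects it. Under the assumptions above, the cost is nil at correlation 0, modest up to about 0.3 (30% against 42% power) and large from 0.5 upward (27% against 55%, with a true error rate of 0.8% in place of 5%). The mismatch itself rests on no assumption; only its size depends on the unknown correlation and effect. The damage is confined to exploratory objective 1.3.1 and is a loss of sensitivity, not a risk of false claims, as long as the correlation is not negative. The correction should be made because the text is plainly wrong and almost free to put right.

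**What to change.** In section 13.5, replace the rank-sum (Mann-Whitney) test for alpha diversity with the Wilcoxon signed-rank test on within-participant differences, post-intervention minus baseline. Make the change before the microbiome data are analysed.

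The cost is a wording change; samples, assays and software stay the same. The one real downside is that baseline samples without a post-intervention partner contribute nothing unless imputed. At correlation 0 that means 31% power against 36% in the 26-and-20 comparison, and the paired test leads once the correlation passes roughly 0.1 to 0.2. The revised sentence should say whether the planned multiple imputation applies to this endpoint.

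A separate and optional clarification concerns beta diversity. The plan says "permutational multivariate analysis of variance (PERMANOVA) will be used" without giving a permutation scheme, and section 9.1 describes triplicate DNA extraction. Here the plan is silent, not wrong. While the paragraph is open, it could state that permutations are restricted within participant, with one profile per participant per visit.
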